In 2022 a meta-analysis performed by (**Grawish et al., 2022**)⁽²³⁾ indicated that DDM as a regenerative biomaterial has potential roles in tissue regeneration. However, in order to confirm these trials, further well-designed analyses are needed, and evaluation of adverse events in observational studies is also needed.

To our knowledge, DDM has not been investigated as scaffold in regenerative endodontics for permanent teeth.

Several studies were evaluate the regenerative effect of DDM at dentin-pulp complex through direct pulp capping technique, and it was found to possess the ability to activate the odontogenic differentiation of stem cells resident in the pulp tissues and induce reparative dentin formation. DDM also considered for alveolar ridge, maxillary sinus floor augmentations, socket preservation, furcation perforation repair, guided bone, and bioroot regenerations as well as bone and cartilage healing ⁽²³⁻²⁷⁾.

Hence, this study will be designed to evaluate regenerative effect of Demineralized Dentin Matrix as a scaffold in comparison to conventional blood clot in immature permanent teeth.

II. The null hypothesis

The null hypothesis is that there are no significance differences in the clinical and radiographic outcomes of regenerative endodontic of non-vital immature permanent teeth following the use of DDM in comparison to a blood clot scaffold.

III. Aim of the study

This study aims to:

Compare the clinical and radiographic outcomes of demineralized dentin matrix scaffold to blood clot scaffold in immature permanent incisors with non-vital pulps for one year.

IV. PICOTS

P: Patients ranging age 7–13years

I: Demineralized Dentin Matrix as a scaffold in Regenerative endodontic procedure

C: Blood clot scaffold Regenerative endodontic procedure

O: Clinical and radiographic success.

T: One year

S: outpatient's clinic of the Pediatric Dentistry and Dental Public Health Department, Faculty of Dentistry, Ain Shams University.

V. Methodology:

i. Study design

A Randomized, Controlled trial with 1:1 allocation ratio

ii. Sample size estimation

A power analysis was designed to have adequate power to apply a two-sided statistical test of the null hypothesis that there is no difference would be found between different groups. By adopting an alpha level of (0.05) a beta of (0.2) i.e. power=80% and an effect size (d) of

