(1.51) calculated based on the results of a previous study ⁽²⁵⁾. the predicted sample size (n) was a total of (24) cases (i.e. 12 cases per group). Sample size was increased by 20% to compensate for possible dropouts during follow-up intervals to be (30) cases (i.e. 10 cases per group). Sample size calculation was performed using G*Power version 3.1.9.7⁽²⁸⁾

iii. Assignment of intervention:

a. Randomization and Allocation concealment.

1- Type: block Randomization, with blocks numbers of 10 and 1:1:1 allocation ratio in to 3 groups

Group I: DDM (study)

Group II: (control) blood clot

Group III: (+ control) blood clot with collagen

2- Sequence generation: the most senior supervisor will generate the sequence of random numbers using online randomization (www.random.org).

Allocation concealment and implementation:

Allocation concealment will be ensured by preparing opaque envelopes containing one number from the generated random sequence for assigned group. The most senior supervisor will select an envelope and reveal the treatment group at the final regeneration visit.

b. Blinding:

double blind study, participants, outcome assessors, statistician will be blinded.

iv. Study setting

This study will be conducted at the Outpatients Clinic at the Department of Pediatric Dentistry and Dental Public Health, Faculty of Dentistry, Ain Shams University.

ii. Study methodology

ethical regulation:

The study protocol will be submitted to the Research ethics committee, Faculty of Dentistry, Ain Shams University for approval.

V. Population

All parent or legal guardian fulfill the eligible criteria will be signed an informed consent before beginning any procedure, explaining detailed treatment procedures, the possible outcomes, comprehensive discussions of the risks, complications, alternative treatment options, follow-up period needed, and sequel of no treatment⁽⁸⁻¹⁴⁾.

Inclusion criteria:

- (1) Age 7–13 years at the time of enrolment.
- (2) Provision of informed consent by one parent or legal guardian.
- (3) At least one immature permanent anterior tooth diagnosed with irreversible pulpitis or pulp necrosis with or without periapical lesions.
- (4) Restorable teeth.
- (5) Compliant patient/parent.
- (6) Patients not allergic to medicaments and antibiotics necessary to complete procedure (ASA 1 or 2).
- (7) Radiologic evidence of open apices (Teeth are considered immature when a minimum of 1 mm apical foramen width is evident)

Exclusion criteria

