- (1) Teeth with root fractures or split roots.
- (2) Presence of root resorptions.
- (3) Presence of periodontal pockets.
- (4) Developmental anomalies
- (5) Presence of periapical radiolucency more than 10 mm
- (6) Tooth with class III mobility.

vi. Clinical Procedures

a. Screening Recruitment

Patients attending the outpatient's clinic of the Pediatric Dentistry and Dental Public Health Department, Ain Shams University will be screened for eligibility. Only patients who met the inclusion criteria and sign the informed consent will be conveniently enrolled in the study until

the predetermined sample size is reached. All examination procedures will be done by the same operator to ensure standardization.

b. Informed Consent

A signed informed consent from parent or legal guardian, and an oral assent to the child, as outlined by the Research Ethics Committee, Faculty of Dentistry, Ain Shams University will be obtained before the conduction of the study.

Grouping:

Eligible immature anterior teeth will be randomly allocated in two groups:

Group I: 10 teeth will be treated with demineralized dentin matrix as scaffold in regenerative endodontic procedure.

Group II: 10 teeth will be treated with conventional regenerative endodontic procedure (blood clot scaffold).

Group III: 10 teeth will be treated with regenerative endodontic procedure (bloodclot and collagen scaffold).

Clinical procedures:

Pre-operative periapical radiograph and cone beam computed tomography CBCT will be taken on the selected non-vital tooth in each child before the beginning of the regenerative endodontic treatment procedure (29, 30).

RET will be carried out according to ASE⁽⁸⁾

First Appointment

- Local analgesia will be delivered (2% lidocaine with 1:100,000 adrenaline).
- Following rubber dam isolation and access cavity preparation, pulp tissue extirpation/debridement
- The root canal system will be minimally instrumented.
- Copious irrigation will be performed, gently with 20ml NaOCl (1.5% NaOCl (20mL/canal, 5 min) using 0.3mm gauge single side vented needles, adjusted 3 mm short of the apex.
- then canal will be irrigated with EDTA (20 mL/canal, 5 min), with irrigating needle that will be positioned about 1 mm shorter than the root end, to minimize cytotoxicity to stem cells in the apical tissues, followed by a final rinse 20 mL sterile saline .

- Canals will be dried with paper points.

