double antibiotic paste, ciprofloxacin (Ciprocin 250mg tablets) and Metronidazole (Flagyl 500mg tablets) in a 1:1 ratio will be mixed with sterile distilled water in a 3:1 ratio, then will be introduced into the root canal systems using 18 G hypodermic needle and will be packed gently down the root canal using a hand plunger, ensuring that there will be no remains coronal to CEJ

- A sterile dry cotton pellet will be placed over the paste after which the tooth will be sealed with 3-4mm of a temporary restorative material.
- Patient will be dismissed for 2 week

Second Appointment (two week after 1st visit)

- Response to initial treatment will be assessed. If there are signs/symptoms of persistent infection, additional treatment time with antimicrobial.
- Local Anesthesia without vasoconstrictor will be administered; dental dam isolation will be achieved.
- Copious gentle irrigation will be performed with 20ml of 17% EDTA, followed by a final rinse 20 mL sterile saline.
- Canals will be dried with paper points.

In group I: teeth will be treated with demineralized dentin matrix as scaffold in regenerative endodontic procedure

Teeth, in this group, will be anaesthetised using a local anaesthetic without vasoconstrictor. Demineralized dentin matrix will be introduced inside the root canal and bleeding will be created into root canal by over-instrumentation by rotating K-file at 2 mm past the apical foramen with the goal of having the entire canal filled with blood to the level of the cemento-enamel junction.

A lightly moistened sterile cotton pellet will be placed into the canal, 3-4 mm apical to the CEJ, for 7-10 minutes to allow blood clot formation.

Placement of the bioactive and restorative materials: A bioactive material such as tricalcium silicate will be placed over the blood clot as a capping material. A 3-4 mm layer of glass ionomer will be gently placed over the capping material.

Followed by resin composite restoration ⁽¹⁶⁾.

In group II: teeth will be treated with conventional regenerative endodontic procedure (blood clot scaffold).

Teeth, in this group, will be anaesthetised using a local anaesthetic without vasoconstrictor. Bleeding will be created into root canal by over-instrumentation

A lightly moistened sterile cotton pellet will be placed into the canal, 3-4 mm apical to the CEJ, for 7-10 minutes to allow blood clot formation.

Placement of the bioactive and restorative materials as mentioned above.

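### The stated contrast is a DDM scaffold versus a blood clot scaffold, but every arm receives an induced clot, so the trial can only show what DDM adds to a clot

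*Protocol*

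**What the plan says.** The Protocol states the contrast in four places before the methods:

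- The introduction closes by saying that the study will "evaluate regenerative effect of Demineralized Dentin Matrix as a scaffold in comparison to conventional blood clot in immature permanent teeth".
- Section II (null hypothesis) refers to outcomes "following the use of DDM in comparison to a blood clot scaffold".
- Section III (aim) is to "Compare the clinical and radiographic outcomes of demineralized dentin matrix scaffold to blood clot scaffold in immature permanent incisors".
- Section IV (PICOTS) gives the intervention as "Demineralized Dentin Matrix as a scaffold in Regenerative endodontic procedure" and the comparator as "Blood clot scaffold Regenerative endodontic procedure".

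The group list under Assignment of intervention labels the experimental arm "Group I: DDM (study", and the Grouping text under Clinical Procedures again describes Group I by DDM alone. Group III, in both lists, is named as a combination of clot and collagen.

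The second-appointment instructions set out what is done. For Group I, "Demineralized dentin matrix will be introduced inside the root canal and bleeding will be created into root canal by over-instrumentation". The blood is meant to fill the canal up to the cemento-enamel junction, 7 to 10 minutes are allowed for a clot to form, and the capping material goes on top of that clot. Group II has induced bleeding and the same clot step, without DDM. Group III has induced bleeding with collagen placed in the canal.

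**The concern.** The governing statements present DDM and the blood clot as two alternative scaffolds. The procedure makes DDM an addition to the clot. These are different questions. One asks whether a clinician could use DDM instead of relying on a clot; the other asks whether putting DDM into a canal that will be filled with blood anyway gives a better result.

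The null hypothesis and aim normally fix how a result is reported. If Group I did better than Group II, the present wording would invite the conclusion that a DDM scaffold is superior to a clot scaffold. The data would support only the conclusion that DDM plus a clot is superior to a clot. If no difference were found, the present wording could lead a reader to treat DDM as a substitute for the clot, although no tooth in the trial would have been treated with DDM in place of one.

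**Working it through.** No planned figure depends on this point, so the check sets the stated contrast beside the procedures and asks which comparisons the arms can identify.

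**Step 1. Contents of each arm (Protocol, Second Appointment; 10 teeth per group from Grouping).**

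| Arm | Label in the group lists | Induced bleeding | Added material | Teeth |
|---|---|---|---|---|
| I | DDM only | yes | DDM | 10 |
| II | blood clot | yes | none | 10 |
| III | blood clot and collagen | yes | collagen | 10 |

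Arms with induced bleeding: I, II and III = 3 of 3. Arms with DDM and no induced bleeding: 0 of 3.

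**Step 2. What the comparisons identify.** Write μ(material, clot status) for the mean outcome, or the success proportion, under a treatment. The arms estimate:

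- Group I: μ(DDM, clot)
- Group II: μ(none, clot)
- Group III: μ(collagen, clot)

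The available contrasts with Group I are therefore:

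- I − II = μ(DDM, clot) − μ(none, clot), the effect of adding DDM to a clot (10 + 10 = 20 teeth).
- I − III = μ(DDM, clot) − μ(collagen, clot), DDM against collagen with a clot in both (10 + 10 = 20 teeth).

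**Step 3. What the stated contrast needs.** Taken as written, a DDM scaffold against a clot scaffold is

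μ(DDM, no clot) − μ(none, clot).

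Its first term is estimated in no arm. The two quantities are related by

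I − II = [μ(DDM, no clot) − μ(none, clot)] + [μ(DDM, clot) − μ(DDM, no clot)].

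The second bracket is what the clot contributes when DDM is present. The design gives no information on it, so no analysis of these arms recovers the replacement contrast from I − II.

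**Step 4. Does the wording show that a clot is meant in Group I?** The Protocol names both components when it labels Group III. Group I has the same structure, a clot plus a material, but its label names only the material. A reader who compares the three labels would conclude that Group I has no clot. Outside the procedure text, no section describes Group I as DDM plus clot or poses an add-on question.

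**Step 5. Is Group III covered?** The null hypothesis, aim and PICOTS name only the clot as comparator. A restatement confined to Groups I and II would leave the third randomised arm outside the stated question, so the correction has to name both comparators.

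**The case against.** The best defence is that the clot is understood. The introduction says that a clot is not a true scaffold but is an essential part of any properly designed regenerative strategy. On that view bleeding belongs to the procedure in every arm, and scaffold means the material added to it. PICOTS fits this reading, because it places DDM within a regenerative endodontic procedure. The Group I instructions are also fully open about the bleeding, and nowhere does the Protocol promise DDM without it.

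Much of this stands. It explains why the arms were built this way and shows that nothing was concealed. It does not correct the hypothesis. The remark is general background, and the same document then calls the clot a scaffold when it names the comparator. The contrast between the Group I and Group III labels also works against the idea that a clot can be taken for granted.

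Three stronger readings are tempting, and the documents do not support them:

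- A reader might infer that the comparison is invalid. It is not. Adding a material to a common background procedure is a sound randomised design.
- A reader might infer that the trial sets out to show that DDM is equivalent to a clot. The Protocol specifies a two-sided test for a difference and states no equivalence or non-inferiority objective. Taking non-significance for equivalence would be a mistake under any label. The narrower point remains: these arms hold no evidence on replacement, whichever way the result falls.
- A reader might infer that the small groups measure the size of this problem. Precision at 10 teeth per group is the same under the present and the corrected wording, so it is a separate matter.

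**Conclusion.** The point holds as a mis-stated contrast. The null hypothesis, aim, PICOTS and Group I label describe DDM versus a clot. The randomised treatments are DDM plus an induced clot, an induced clot alone, and an induced clot plus collagen. The trial can estimate DDM's effect on top of a clot, against nothing added or against collagen, and never DDM instead of a clot.

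Its size is qualitative: 3 of 3 arms include induced bleeding, 0 of 3 give DDM without it, and all four opening statements of the contrast leave the clot off the DDM side. No sample size, power or analysis figure changes. The conclusion rests on the Protocol text alone and assumes only that the second-appointment procedures are carried out as written.

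This is more than a clerical slip, because it decides what the trial may conclude. It is less than a design fault, because the randomised comparisons are valid. It should be corrected before results are reported.

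**What to change.** Amend the wording as follows:

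- In the introduction's closing sentence, null hypothesis, aim and PICOTS, describe the intervention as DDM plus induced blood clot, compared with induced blood clot alone and with induced blood clot plus collagen.
- Relabel Group I in the same way in the group list and the Grouping text, so that it matches the form already used for Group III.
- State that conclusions are limited to the effect of DDM added to an induced clot, and that the trial makes no claim that DDM replaces a clot or is an alternative to one.

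The cost is a text amendment, reviewed by the ethics committee as the Protocol's section on amendments requires. Arms, procedures, analysis and sample size do not change. The downside is a narrower claim, which is the one the randomised arms can support.

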In group III: teeth will be treated with conventional regenerative endodontic procedure (blood clot and collagen scaffold).

Teeth, in this group, will be anaesthetised using a local anaesthetic without vasoconstrictor. Bleeding will be created into root canal by over-instrumentation

A collagen will be placed into the canal, apical to the CEJ.

Placement of the bioactive and restorative materials as mentioned above

e. Follow up

Clinical and Radiographic examination will be carried out during follow up period^(15, 16).

1- Clinical evaluation: Treatment success will be assessed using following criteria of success.

Criteria of success: Absence of

- Pain
- Soft tissue swelling
- Soft tissue inflammation
- Sinus tract
- tenderness to percussion
- tooth mobility

2- Radiographic evaluation:

A-Conventional radiographic evaluation:

Criteria of success:

- Apical foramen width reduction
- Increased dentinal wall thickness
- Increased root length
- Conventional radiograph showing progress bone healing and presence of a normal periodontal ligament space.
- Reduction in size of the lesion.

B- CBCT evaluation:

- CBC with limited field of view will be carried out at 12 month to asses dentin width and length^(23, 28)

f. Outcome measurement

Outcome	assessment	Assessment method
Primary outcome	1- pain 2-pain percussion 3-pathological mobility 4- gingival becket	1-visual assessment 2-percussion test 3-blunt ends of two examination mirrors 4-graduated metal periodontal probe
Secondary out com	1-Root length 2-Root dentinal thickness 3- Apical foramen width 4- Total radiographic root area (absence of internal and external root resorption, widening of periodontal ligament space, new preabical radiolucencies or enlargement of pre-existing lesion, pulp canal calcification)	Digital periapical radiograph examination with using paralleling device
Secondary outcome	Increased root wall thickness and increased root length.	CBCT with limited field of view

VII. Statistical analysis

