Categorical data will be represented as frequency (n) and percentage (%) and will be analyzed using chi square test. Numerical data will be explored for normality by checking the data distribution, calculating the mean and median values and using Kolmogorov-Smirnov and Shapiro-Wilk tests. If the data was found to be normally distributed, it will be presented as mean and standard deviation values and paired t-test will be used for the analysis. If the assumption of normality was found to be violated; the data will be presented as median and range values and will be analyzed using Signed rank test. The significance level will be set at $p \leq 0.05$ for all tests. Statistical analysis will be performed with IBM SPSS Statistics Version 26 for Windows.

VIII. Study timeline

This study will be conducted from October 2023 to October 2024.

X. Patient withdrawal

- Patients who aren't willing to continue in the study will have the right to quit at any time without loss of any benefits.
- Patients who don't comply with the oral hygiene measures given will be excluded from the study and will be offered to continue dental treatment at the departments' outpatient clinic.
- Any adverse event will be recorded and managed promptly. In addition, in failure occurs, the use of the experimental material will be stopped and patients will be treated with another modality.

[figure not shown]
xi. Data management

Patient information will be guarded as confidential information that should never be revealed at all times.

All information will be kept as a hard and soft copy.

xii. Adverse event reporting

Regenerative treatment is not expected to have any adverse side effects on health but if failure occurs in the regenerative treatment, conventional regenerative endodontic treatment will be fabricated.

xiii. Ethics and dissemination

a. Research ethics approval:

This protocol and the template informed consent form contained in Appendix are written following the guidelines outlined by the Research Ethics Committee and Institutional Review Board, Faculty of Dentistry, Ain Shams University.

b. Protocol amendments:

In case of protocol modifications, the Research Ethics Committee and Institutional Review Board, Faculty of Dentistry, Ain Shams University will review and approve the changes of protocol before proceeding and implementation of changes.

c. Informed consent:

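### Three of the five radiographic success criteria, and the CBCT outcome, count any favourable change with no minimum, so a tooth with no root growth meets each about half the time on measurement error alone

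*Protocol*

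**What the plan says.** Under IV. PICOTS the protocol gives the outcome as "O: Clinical and radiographic success". Radiographic success is defined under e. Follow up, 2- Radiographic evaluation, by five listed criteria. Three concern root development: "Apical foramen width reduction", "Increased dentinal wall thickness" and "Increased root length". The other two concern bone healing with a normal ligament space, and shrinkage of the lesion. No criterion carries a value in mm, a percentage or a repeatability limit, and the protocol does not say whether all five or only some must be met.

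The table under f. Outcome measurement makes clinical signs the primary outcome. It has two secondary radiographic rows:

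- The periapical row names root length, dentinal thickness and foramen width as plain quantities, assessed by "Digital periapical radiograph examination with using paralleling device".
- The CBCT row is worded by direction: "Increased root wall thickness and increased root length". The CBCT scan "will be carried out at 12 month to asses dentin width and length", and a pre-operative scan is also planned (Clinical procedures).

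Under VII. Statistical analysis, "Categorical data will be represented as frequency (n) and percentage (%) and will be analyzed using chi square test". A separate path covers numerical data.

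**The concern.** Root length, wall thickness and foramen width are each read from two images taken up to a year apart, and every reading carries error. When the true change is zero, the sign of the measured change is decided by error alone. A rule that scores any favourable sign as success therefore credits regeneration to teeth that have not grown, and it scores a trivial change the same as real maturation.

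This raises success percentages in every arm and narrows the gap between them. If both arms grow, nearly every tooth passes and the rule can hardly separate the scaffolds. In a 30-tooth trial whose aim includes comparing radiographic outcomes, that favours a finding of no difference. Because the criteria are written into the protocol, this is a rule fixed badly and not a detail left to a later plan.

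**Working it through.** **Inputs from the protocol.** Two-sided alpha 0.05 and power 80%; d = 1.51; totals of 24 and, after 20% dropout, 30; three arms at 1:1:1 with 10 teeth each; chi-square for categorical data.

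**Assumptions, not in the documents.** Reading error is symmetric, with the same distribution at both times. For the power comparison, the measured change is normal with SD s in each arm.

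**The plan's own figure.** At d = 1.51 a two-sided two-sample t-test needs 8 per group (power 80.2%). Then 3 × 8 = 24 and 24/0.8 = 30, so 10 per arm reproduces. The stated 12 per group does not, since it would give 94.2% power. That is a separate matter, and 10 per arm is used below.

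**Step 1: one criterion, no true growth.** With errors e1 and e2 at the two readings, P(pass) = P(e2 − e1 > 0) = 50%, whatever the size of the error. Departures from the assumption:

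- Readings rounded to 0.5, 1 or 2 times the single-reading SD, with ties failing: 43%, 36%, 26%.
- Systematic bias of −0.5 to +0.5 SD of the difference: Φ(−0.5) = 31% to Φ(0.5) = 69%.

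**Step 2: the three root-development criteria together.** For error correlation ρ, P(all three) = 1/8 + 3·arcsin(ρ)/(4π), and P(at least one) = 1 − P(all three).

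| ρ | All three required | Any one suffices |
|---|---|---|
| 0 | 12.5% | 87.5% |
| 0.5 | 25% | 75% |
| 0.9 | 39% | 61% |

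These figures leave out the bone-healing and lesion criteria, so they are not overall success rates.

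**Step 3: power at 10 per arm.** For true growth g, P(pass) = Φ(g/s). A difference of 1.32 SD is what a t-test detects with 80% power at this size. Chi-square power is by exact enumeration, without continuity correction.

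| Control growth | True difference | Pass rates | t-test on change | Chi-square on any increase |
|---|---|---|---|---|
| 0 | 1.32 SD | 50% v 91% | 80% | 49% |
| 0 | 1 SD | 50% v 84% | 56% | 33% |
| 1 SD | 1.32 SD | 84% v 99% | 80% | 5% |

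**Step 4: effect of a minimum change.** With a cut at k SDs of the difference between two readings, a no-growth tooth passes with probability 1 − Φ(k): 50% at k = 0, 15.9% at k = 1, 5.0% at k = 1.645 and 2.5% at k = 1.96. The last is the repeatability limit, 1.96 × √2 × the within-reader SD.

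Taking s to be measurement error only, with a true difference of 1.32 SD, P(pass) = Φ(g/s − 1.96):

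- Control growth 0: 2.5% v 26%. Chi-square power is 20%, against 49% without the cut.
- Control growth 1 SD: 17% v 64%. Chi-square power is 57%, against 5% without the cut.

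The cut removes most false passes, but its effect on power can go either way. Both yes/no versions stay below the 80% of the t-test.

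**The case against.** The strongest reply is that the protocol already plans the measurements. The periapical row lists the three quantities with no success cut, CBCT is taken before treatment and at 12 months, and the statistics section has a numerical path. The power loss in step 3 therefore arises only where the quantities are reduced to yes/no. This stands, and it limits the point to the success criteria and the CBCT row. It does not remove the point, because the periapical row does not withdraw the criteria and the CBCT row is worded as an increase. The numerical path also names only paired tests, so the protocol does not say that the changes are compared between arms.

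Four stronger readings are tempting, and the documents do not support them:

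- **An overall false success rate.** A reader might take 12.5% or 87.5% as the trial's figure. The combination rule is unstated and two of the five criteria are not of this kind, so no overall rate can be computed.
- **Power falling to 31% (or 19% at 1 SD).** Fisher's exact test gives those values, but the protocol names chi-square, which gives 49% and 33%. Part of the extra loss is Fisher's conservatism at this size: with 50% in both arms it rejects 1.3% of the time, against 4.2% for chi-square.
- **Bias towards DDM, or a real DDM effect necessarily hidden.** The protocol plans blinded assessors. Error common to all arms dilutes a contrast and does not favour one arm, and an effect could still show in the numerical outcomes.
- **A minimum change restores power.** Step 4 shows that it need not. Much of the loss comes from dichotomising.

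It is also fair to say that 50% is the central case of an assumption. However, within the range examined the false-pass rate per criterion never falls below about a quarter.

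**Conclusion.** The point holds for three of the five radiographic success criteria and for the CBCT outcome row. As written, they let a tooth with no growth pass each criterion about half the time under unbiased, finely graded error, with a range of 26% to 69% across the rounding and bias examined. Yes/no success is inflated in all arms and the between-scaffold contrast is weakened. In the scenarios computed, power at a 1.32 SD difference is 49% or about 5%, where a t-test on the change has 80%.

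The consequence is limited. The outcomes concerned are secondary, the primary outcome is clinical, and analysis of the listed periapical measurements as numbers is untouched. The power figures rest on normal changes with equal SD, 10 evaluable teeth per arm and the assumed control growth, none of which the documents supply. The change is worth making before the radiographic data are analysed.

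**What to change.** 1. Under e. Follow up and f. Outcome measurement, state that the radiographic comparison, for periapical and CBCT images alike, is the measured change in mm (12 months minus pre-operative), compared between arms.
2. Reword the CBCT row so that it names the change in wall thickness and root length, not an increase.
3. Keep radiographic success as a descriptive summary only, and say how its criteria combine. If it is reported, count a change in length, thickness or foramen width only when it exceeds the repeatability limit, 1.96 × √2 × the within-reader SD. Estimate that SD by having the same blinded assessor re-measure a subset of the images already taken. Re-reading one image captures reading error but not positioning differences between exposures, so treat the limit as a lower bound.

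The cost is a wording change and a few hours of re-measurement, with no extra visits or exposures. Reported success percentages will be lower. The thresholded yes/no outcome has less power than the present rule when control growth is near zero (about 20% against 49% by chi-square), which is why it should not carry the inference.
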